Developing and Evaluating In-Home Supportive Technology for Dementia Caregivers, Phase
IIB
R44AG059458-03
April 14, 2022

Statistical Analysis Plan

Primary Outcomes

All caregivers—regardless of randomized study condition—complete questionnaires on three separate occasions during this study: baseline, 3-months, 6-months. The four outcome measures include changes over the 6-month study period for the following scales: Zarit Burden Interview-Short Form, a questionnaire measuring caregiver burden (Zarit, Reever, & Bach-Peterson, 1980). 12 items are rated on 0-4 scale. Range: 0-48. No subscales. Higher scores represent worse outcomes; Center for Epidemiological Studies Depression Scale (CES-D), a questionnaire measuring depression (Radloff, 1977). 20 items are rated on a 0-3 scale and summed (range = 0-60). There are no subscales. Higher scores represent worse outcomes. The clinical cut-off is usually set at a score of 16; Beck Anxiety Inventory (BAI), a questionnaire measuring anxiety (Beck, Epstein, Brown, & Steer, 1988). 20 items are rated on a 0-3 scale and summed (range= 0-60). Higher scores indicate worse outcomes. There are no subscales. A score greater than 36 is considered to be clinically significant.; and Satisfaction with Life Scale, a questionnaire measuring overall life satisfaction and well-being (Diener, Emmons, Larsen, & Griffin, 1985). 5 items scored on a 1-7 scale and summed (Range = 5-35). Lower scores indicate worse outcomes. A score of 20 is considered neutral with higher scores considered increasingly more satisfied and lower scores considered increasingly more dissatisfied.

Statistical Methods

Design: Caregivers will be randomized into two groups: Active In-Home Technology System and Waiting Control. Subjects will be randomized 3:1. Randomization of participants in each group will be determined by People Power employees. With a total N of 400 caregivers in two conditions and measures repeated three times, a comparison between groups using ANOVA will have .80 power to detect a medium effect size at $p=.05$.

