Analysis: Descriptive statistics will be used to summarize all the clinical characteristics and demographic outcomes. These will be summarized overall, by treatment group, by assessment time, and by treatment group and time. Continuous variables will be summarized using means, standard deviations, and ranges. Categorical data will be summarized by number and percent. To evaluate the treatment effects, we will use repeated measures ANOVAs. The other predictors will be treatment group, and time (baseline, 3-months, and 6-months for caregiver outcomes). To evaluate treatment effects, an interaction term between treatment group and time will be included to examine treatment group-related differences in the assessments for each outcome. Each significant interaction will be followed up with paired t-tests to examine treatment differences at each set of time points. Although this study involves 4 outcomes, we do not plan formal multiple comparison adjustments if the results fit a coherent pattern that is consistent with the context of

similar studies. In this case, each result will reinforce the other, rather than detracting from one another, as required by formal multiple comparisons adjustments such as Bonferroni. Conversely, if only one or a very few measures reach statistical significance and their directions and/or magnitudes do not coherently fit with our a prior expectations, then we will note that the result(s) with $p < 0.05$ lack plausibility and could be due to chance, despite meeting the conventional cutoff for statistical significance.

Missing Data: If subjects either cannot or refuse to complete surveys we will use a sensitivity analysis approach in dealing with these missing data by performing analysis with 2 versions of scores: 1) with missing item interpolated using mean replacement by group, and 2) only using responses with 0% missing data. If the results differ for the two approaches, then we will report on the differences.

REFERENCES

Bedard, M., D.W. Molloy, L. Squire, S. Dubois, J.A. Lever, and M. O'Donnell, The Zarit Burden Interview: a new short version and screening version. *Gerontologist*, 2001. 41(5): p. 652-7.

Radloff, L.S., The CES-D scale: A self-report depression scale for research in the general population. *Applied Psychological Measurement*, 1977. 1: p. 385-401.

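### The SAP's chance caveat can be triggered by direction alone, so an isolated significant worsening would be discounted where an isolated improvement of the expected size would not

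*SAP*

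**What the plan says.** The SAP lists four primary outcomes: "The four outcome measures include changes over the 6-month study period for the following scales", namely caregiver burden, depression, anxiety and life satisfaction. It states which direction is worse on each; for the anxiety inventory, "Higher scores indicate worse outcomes". Treatment effects are judged through the group-by-time term of a repeated measures ANOVA: "an interaction term between treatment group and time will be included to examine treatment group-related differences in the assessments for each outcome".

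The Analysis paragraph then gives two rules for reading the four results:

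- **Coherent pattern.** "we do not plan formal multiple comparison adjustments if the results fit a coherent pattern that is consistent with the context of" similar studies. The results are then taken to reinforce one another.
- **Isolated and unexpected.** The second rule applies "if only one or a very few measures reach statistical significance" and "their directions and/or magnitudes do not coherently fit with our a prior expectations". The team will then note that the results with p < 0.05 "lack plausibility and could be due to chance, despite meeting the conventional cutoff for statistical significance".

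The expectations are not stated in either document, and no number is given for a very few. Nothing is said about a significant result that is unfavourable to the active arm.

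**The concern.** A caveat about chance is reasonable when four scales are tested without adjustment. But chance produces isolated favourable and isolated unfavourable results equally often, so a caveat that rests on chance should not depend on sign. This one does. The and/or wording makes an unexpected direction sufficient for the discount.

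The technology is meant to support caregivers, so the unexpected direction is presumably worsening. In-home monitoring could plausibly raise anxiety or burden in some households. If that happened on one scale, the plan commits the authors in advance to describing the finding as lacking plausibility. The supplied protocol and SAP describe no adverse-event or other harm analysis that would treat it differently. The added questionnaire items at 3 and 6 months concern usefulness, not harm. At stake is a published conclusion that leans away from an isolated harm.

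**Working it through.** **The plan's own figure.** The SAP's Design paragraph states .80 power for a medium effect with N = 400. It gives no number for medium. Taking d = 0.5 as an assumption, with 3:1 allocation and unit SD:

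- √(1/300 + 1/100) = 0.1155
- 0.5/0.1155 = 4.33, so two-sided power = Φ(4.33 − 1.96) = .991
- Power of .80 is reached at (1.96 + 0.84) × 0.1155 = 0.32 SD

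The stated .80 is not reproduced under that reading; it would be conservative. The present point does not depend on it.

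**Inputs.** From the documents: 300 active and 100 control, four scales, p<.05. Assumed: SD 1, baseline-to-6-month correlation r of .5 to .7, no dropout, and a two-sided 5% test of the between-arm difference in change. The SAP does not state sidedness, but its interaction F test has no direction.

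**Chance of detecting a true worsening on one scale.** SE = √(2(1 − r)) × √(1/300 + 1/100); detection = Φ(d/SE − 1.96).

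| r | SE (SD units) | d = 0.25 | d = 0.35 |
|---|---|---|---|
| .5 | .1155 | .581 | .858 |
| .6 | .1033 | .677 | .923 |
| .7 | .0894 | .798 | .975 |

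At d = 0.20 the range is .41 (r = .5) to .61 (r = .7), so detection depends strongly on the size of the effect.

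**Same check with the SAP's 2-df interaction** (large-sample approximation, equal correlation between visits). For a shift d at both 3 and 6 months, the noncentrality is (2/3)d²/[(1 − r)(1/300 + 1/100)]. At d = 0.35 this is 12.25 for r = .5 and 20.4 for r = .7, giving power of about .89 and .99. The conclusion is unchanged.

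**How often the discounting rule would then apply.** Read a very few as at most two of the four scales, and let the other three have no true effect. With r = .5, simulation over between-scale correlations of 0 to .7 gives:

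| True worsening | Significant and unfavourable | Of all trials, also at most two scales significant |
|---|---|---|
| 0.3 SD | .74 | .72 to .73 |
| 0.4 SD | .93 | .91 to .93 |

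So nearly every detected isolated worsening would meet the rule on count and direction.

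**Comparison with chance.** With no effect, a named scale is significant in the harmful direction 2.5% of the time. For at least one of four scales the rate is 1 − .975⁴ = 9.6% if they are independent, and by simulation 7.8% and 6.5% at between-scale correlations of .5 and .7. Likelihood ratios for a named scale:

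- 0.35 SD: .858/.025 = 34 to .975/.025 = 39
- 0.25 SD: .581/.025 = 23 to .798/.025 = 32

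For any of four scales, dividing the lower detection rate by the largest null rate gives .858/.096 = 8.9 at 0.35 SD and .581/.096 = 6.1 at 0.25 SD.

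**The case against.** The strongest defence is that this is an interpretive caveat standing in for multiplicity adjustment. With four independent unadjusted tests, the chance of at least one false positive is 1 − .95⁴ = 18.5%, so some caution about isolated results is warranted. The trigger also includes magnitude, so a favourable result of unexpected size could be discounted too. A single favourable scale beside three null ones fits neither rule clearly, and worsening on most scales falls outside the isolated-result rule.

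All of that stands, and it limits what can be claimed. Four stronger readings that a reader might infer are not supported:

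- **That the trial could never conclude harm.** The SAP says such results could be due to chance, not that they are, and it says they will be noted. Scores are also summarised by group and time regardless.
- **That the defect has nothing to do with multiplicity and would arise with a single outcome.** The rule is introduced because there are four outcomes, and it is triggered by how few are significant.
- **That the asymmetry is written into the plan as a stated expectation of benefit.** The expectations are not given; improvement is inferred from the purpose of the technology.
- **That ratios such as 34 to 1 are the odds that harm is real.** They compare how often p<.05 arises with and without a given worsening. Odds would also need a prior.

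Nor can one say that the whole trial record lacks harm reporting: consent pages are not in the supplied text. What the defence does not remove is that direction is an explicit and sufficient ground for the discount, with no exception for worsening.

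**Conclusion.** The concern holds as a bias in interpretation. Followed as written, the rule discounts an isolated significant worsening because of its sign, and does not discount an isolated improvement of the expected size. This rests on reading improvement as the expected direction and a very few as one or two scales.

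The discount would often fall on results that carry real evidence. Under the stated assumptions, a 0.35 SD worsening is detected in 86% to 97% of trials and a 0.25 SD worsening in 58% to 80%, against 2.5% for a named scale under no effect. Dropout or a lower pre-post correlation would reduce the detection figures. The asymmetry itself comes from the wording and depends on none of these numbers. The paragraph should be changed before the results are known.

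**What to change.** Remove direction as a reason to call a result implausible, and state the expected direction for each of the four scales in advance. Replace the sentence on isolated results with:

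> Any outcome with a significant group-by-time interaction (p<.05) in which the between-arm difference in change from baseline is unfavourable to the active arm will be reported in the main results as a possible harm, with that difference and its 95% CI. Caveats about chance from testing four outcomes will be applied in the same way to favourable and unfavourable results.

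The text should name the visit at which the sign is read; 6 months matches the SAP's definition of the outcomes as changes over the study period. The between-arm difference and its interval need to be added as an output, because a paired t-test compares time points within an arm and does not supply them.

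The cost is one SAP paragraph and no new data. The downside is that, with no true effect, there is roughly a 6.5% to 10% chance of reporting a false harm signal on at least one of the four scales. The confidence interval and the even-handed caveat let readers weigh such a signal.

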After completion of the first questionnaire and successful installation of the system, caregivers randomly assigned to the active condition will be mailed a check of \$100. Qualtrics questionnaires will be sent via email to caregivers in both research conditions at baseline, 3 months, and 6 months. Upon completion of the final questionnaire at 6 months, caregiver participants will be mailed a \$50 check to compensate for their time completing questionnaires. A member of the research team will contact the caregivers to let them know they are welcome to uninstall and dispose of the system, or they may choose to keep any and all sensors, devices, or equipment in their home. For those who choose to keep equipment or devices, they will not be charged any cost and we will end our data collection of any related devices and will not ask that they complete any additional questionnaires regarding their usage of the system, sensors, or equipment (i.e., their participation in this study is complete). Caregivers randomly assigned to the waiting control condition will be mailed a check for \$25 upon completion of the first questionnaire. After completion of the 3 and 6 month questionnaires, caregivers will be mailed a check for \$50 and offered an opportunity to enroll in an additional 6-month study. If they enroll, they will be mailed the Presence Care system for them to self-install and have all sensors activated. They will also be asked to complete the questionnaires at 9-months and 12-months. Following the completion of this additional 6-month study, caregivers will be mailed a check for \$125 for the 9 and 12 month questionnaires, as well as the installation to compensate for their time and effort.

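### The missing-data rule plans two analyses, ranks neither and leaves its scope open; the group-mean version understates standard errors, by an amount that depends on the reading and on dropout rates the documents do not give

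*SAP*

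**What the plan says.** The plan for missing data is the short Missing Data paragraph of the SAP's Statistical Methods.

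- **Trigger:** "If subjects either cannot or refuse to complete surveys we will use a sensitivity analysis approach".
- **Method:** "performing analysis with 2 versions of scores", namely "with missing item interpolated using mean replacement by group, and 2) only using responses with 0% missing data".
- **If they differ:** "If the results differ for the two approaches, then we will report on the differences".

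The scores feed the Analysis paragraph: "To evaluate the treatment effects, we will use repeated measures ANOVAs", where "an interaction term between treatment group and time will be included" to carry the treatment comparison for each of four outcomes. The power statement in the Design paragraph counts everyone at every visit ("With a total N of 400 caregivers in two conditions and measures repeated three times") and makes no allowance for loss. Neither document gives an expected dropout rate, a limit on how much may be filled, or a variance correction.

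**The concern.** Three things are left open.

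1. **Which analysis decides.** Both versions are called a sensitivity approach, but there is no primary analysis for them to be sensitive to. Reporting a difference discloses it; it does not say which result stands. Four outcomes in two versions give eight interaction tests, with the choice within each pair open after results are seen.
2. **What is filled.** The trigger concerns surveys not completed; the remedy concerns an item. The SAP does not say whether a wholly missed survey is filled, whether the group mean is taken per visit, or whether *responses* means single surveys or caregivers complete at all visits.
3. **What filling does to the test.** A group mean counts as an observation but contributes no within-group variation. The error term shrinks while the nominal sample size stays full, so p-values are too low.

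The stake is the error rate of one version, lost data in the other, and no stated way to choose between them.

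**Working it through.** **The plan's own figures.** None bears directly on missing data. The nearest is .80 power for a medium effect. With 100 and 300 caregivers (Protocol, Randomization), a simple two-sided comparison of means has .80 power at (1.96 + 0.84) × √(1/100 + 1/300) ≈ 0.32 SD, and 99.1% at 0.5 SD. The SAP puts no number on medium. That is a separate matter; here it only shows why more than one effect size is needed below.

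**Inputs from the documents:** arms of 300 and 100, three visits, group-by-time F test at .05. **Assumed:** missing rates, within-person correlation, effect sizes, a two-sided test.

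**Mechanism, one visit.** With a share *p* of an arm of size *n* missing at random, the mean has true variance σ²/[n(1−p)]. After filling, the reported variance is about (1−p)σ²/n. The ratio of reported to true is (1−p)², so the standard error is (1−p) times what it should be. A nominal 5% test then rejects at 2Φ(−1.96 × 0.80) = 11.7% for p = 20%, and 2Φ(−1.96 × 0.75) = 14.2% for p = 25%. The group-by-time test is milder because baseline is taken as complete.

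**Whole surveys filled with group-by-visit means.** Simulated null trials, 10,000 per case, compound symmetry, Monte Carlo error 0.2–0.4 points. Entries are % false positives when none / half / all of the 6-month dropout is already missing at 3 months.

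| Missing at 6 months | Correlation 0.5 | Correlation 0.7 |
|---|---|---|
| 10% | 6.5 / 6.6 / 7.1 | 6.2 / 6.9 / 7.2 |
| 20% | 7.8 / 9.1 / 10.3 | 7.6 / 8.8 / 10.5 |
| 25% | 8.9 / 10.3 / 12.9 | 9.2 / 10.3 / 11.7 |

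Complete cases gave 4.6–5.4% and a mixed model 4.5–5.3%. Separate runs with correlation down to 0.3, an autoregressive structure and independently missed visits gave 5.4–7.9% at 10%, 7.5–11.1% at 20% and 8.1–13.4% at 25%. A Greenhouse-Geisser correction did not remove the excess. At 5% missing the range was 5.1–6.6%.

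With 25% missing at 6 months, depending on the 3-month score equally in both arms, complete cases gave 4.8–5.2%, mean replacement 8.5–9.6% and the mixed model 4.5–5.5%.

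**Only items filled.** With a share *p* of items missing independently and filled by group-by-visit item means, the reported variance is again (1−p)² of the true one. For the 2-df interaction test in large samples, the false-positive rate is 0.05 raised to the power (1−p)²:

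- 2%: 0.05^0.9604 = 5.6%
- 5%: 0.05^0.9025 = 6.7%
- 10%: 0.05^0.81 = 8.8%

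A simulation of a 12-item scale (error about 0.3 points) gave 6.2%, 6.5% and 8.4%, against 5.7%, 4.7% and 5.1% in the same trials with nothing missing. Prorating from the person's own answers gave 5.6%, 4.7% and 4.9%. On this reading, wholly missed surveys have no rule except deletion.

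**Data kept by the 0%-missing version, 2% of items missing independently:**

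| | Burden, 12 items | CES-D, 20 items |
|---|---|---|
| Single survey complete | 0.98^12 = 78% | 0.98^20 = 67% |
| Caregiver complete at three visits | 0.98^36 = 48% | 0.98^60 = 30% |

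**How often the two versions disagree at .05** (whole-survey reading, 20–25% missing):

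- No effect: about 6–10% under dropout patterns, and up to 13.7% if follow-up visits are missed independently.
- 0.25 SD at both follow-ups: about 14–23%. Here the mixed model has about 2–11 points more power than complete cases.
- 0.5 SD: 0–2%, since both versions have about 98–100% power.

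**The case against.** The strongest reply is that the remedy wording points to gaps inside a questionnaire: it speaks of an item, of versions of scores, and of a percentage missing. An incomplete survey can be a partly finished one. Read that way, group-mean filling at 2% of items does negligible harm. In addition, both versions will be run and differences reported, and the 0%-missing version is valid under random or arm-equal dropout, so an inflated result would appear beside a sound one. Naming that version primary and defining the terms would close the gap in the text.

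Most of this stands, and it limits the point. It does not remove it: under the item reading, missed surveys are left to deletion, and under either reading no result is said to decide. Making the 0%-missing version primary would hold the error rate in the scenarios checked, but at the cost of usable data.

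Four stronger inferences are not supported:

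- **That the trial will run at 8–13% false positives.** This needs whole-survey filling, which the SAP does not clearly state, and about 25% dropout, which is assumed. At 5% missing the excess is at most about 1.5 points.
- **That this rule settles the result for all four outcomes.** In about 90–94% of null trials at 20–25% dropout the versions agree, and at 0.5 SD they almost always do.
- **That only 48% or 30% of caregivers would remain.** That takes the strictest meaning of *responses* and independent skipping; if skips cluster within people, the loss is smaller.
- **That dropout biases the comparison in a known direction.** Complete cases can fail if dropout depends on scores differently by arm. Early payments differ between arms, but both are paid \$50 at the end (Protocol, Contact initiated by study staff: "Upon completion of the final questionnaire at 6 months, caregiver participants will be mailed a" check of that amount; the control arm likewise after its 3- and 6-month surveys). Nothing gives the size or sign of any bias.

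**Conclusion.** The point holds as a specification gap that should be fixed, with a conditional effect on error rates. The gap is plain from the text: two unranked analyses, no deciding rule, undefined scope. That group-mean replacement understates standard errors follows from arithmetic under either reading; only the size is uncertain.

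Conditional on whole surveys being filled with group-by-visit means, false positives are about 5–6.5% at 5% missing, 6–8% at 10%, 7–11% at 20% and 8–13% at 25%. Conditional on item filling only, they are about 5.6%, 6.7% and 8.8% at 2%, 5% and 10% of items missing. These figures assume missingness at random and equal in both arms. Filling with a mean pooled over visits was not examined. Because the second version is always shown alongside, the remaining harm is an open choice between two answers, not a hidden inflated result.

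**What to change.** Change the SAP before outcome data are examined by arm:

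1. Give separate rules for missing items and missed surveys.
2. For each outcome, make the primary analysis a likelihood-based mixed model on all randomized caregivers using every observed visit, with arm, visit, arm-by-visit and a pre-stated covariance structure such as unstructured. Multiple imputation using arm and all visits is an acceptable alternative.
3. Replace group-mean filling of isolated items by proration from the person's own answers, above a pre-stated minimum number answered.
4. Keep the 0%-missing analysis as a labelled sensitivity analysis, and say whether it means complete surveys or complete caregivers.
5. State that the conclusion rests on the primary analysis and that differences from the sensitivity analysis will be reported.

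The cost is SAP wording, standard software and slightly more analysis work, with no new data. Intervals will be wider than under mean replacement, which is the correction intended. The mixed model and multiple imputation still assume that missingness depends only on observed data.
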